8.4.3 UNANTICIPATED PROBLEM REPORTING

All possible unanticipated problems will be reported to the IRB within five (5) days of receiving notice of the event if the event requires immediate intervention to prevent serious harm to participants or others. All other possible unanticipated problems will be reported to the IRB as soon as possible and no later than ten (10) business days from the date of the event or from the date the investigator is notified of the event.

Investigators must promptly report (according to the above schedule) the following events to the IRB if the events occur within thirty (30) days of participants' active participation:

- Adverse events which in the opinion of the principal investigator are both unexpected and related.
- An unanticipated event related to the research that exposes individuals other than the research participants (e.g., investigators, research assistants, students, the public, etc.) to potential risk
- Information that indicates a change to the risks or potential benefits of the research. For example:
- An interim analysis or safety monitoring report indicates that frequency or magnitude of harms or benefits may be different than initially presented to the IRB.
- A paper is published from another study that shows that the risks or potential benefits of your research may be different than initially presented to the IRB.
- A breach of confidentiality.
- Incarceration of a participant in a protocol not approved to enroll prisoners.
- Change to the protocol taken without prior IRB review to eliminate an apparent immediate hazard to a research participant.
- Complaint of a participant when the complaint indicates unexpected risks or cannot be resolved by the research team.
- Protocol violation (meaning an accidental or unintentional change to the IRB approved protocol) that harmed participants or others or that indicates participants or others may be at increased risk of harm.
- Event that requires prompt reporting to the sponsor.
- Sponsor imposed suspension for risk.
- Any other event that indicates participant or others might be at risk of serious, unanticipated harms that are reasonably related to the research.

8.4.4 EVENTS OF SPECIAL INTEREST

Not Applicable.

8.4.5 REPORTING OF PREGNANCY

Subjects found to be pregnant during preoperative testing or during the course of treatment will be excluded until not pregnant at which point re-evaluation can occur at the discretion of the PI.

8.5 STUDY HALTING RULES

Use and implantation of the neurostimulator system will be halted when three grade 3 AEs determined to be “probably related or definitely related.” The PI will notify the study sponsor and IRB immediately when the third grade 3 event is reported and enrollment screens will stop accepting new study participants. The study sponsor will inform the FDA of the temporary halt and the disposition of the study.

8.6 SAFETY OVERSIGHT

Safety oversight will be the responsibility of the principal investigator.

9 CLINICAL MONITORING

Clinical site monitoring will be performed by the study monitor. The appointment and responsibilities of the study monitor are defined in section 13.5.

10 STATISTICAL CONSIDERATIONS

10.1 STATISTICAL AND ANALYTICAL PLANS

This study explores the effect of epidural spinal cord stimulation on volition movement and autonomic function and represents one of the first studies with little preliminary evidence. The statistical plan is delineated for the primary, secondary, and exploratory outcomes below.

10.2 STATISTICAL HYPOTHESES

Primary Endpoint

Volitional Response Index Magnitude

The hypothesis of the primary outcome VRI magnitude is that epidural spinal cord stimulation will provide a higher VRI magnitude than sham.

H0: mean treatment VRI magnitude = mean sham VRI magnitude

Ha: mean treatment VRI magnitude \neq mean sham VRI magnitude

Secondary Endpoints

Standing Training Assessment

Hypothesis: standing power will be improved with epidural stimulation

H0: mean treatment standing power = mean sham standing power

Ha: mean treatment standing power \neq mean sham standing power

Sympathetic Skin Responses (SSR)

Hypothesis: SSR will be unchanged by epidural stimulation

H0: mean treatment SSR = mean sham SSR

Ha: mean treatment SSR \neq mean sham SSR

Blood pressure

Hypothesis: blood pressure will be increased with epidural stimulation

H0: mean treatment BP = mean sham BP

Ha: mean treatment BP \neq mean sham BP

Cerebrovascular Assessment

Hypothesis: epidural stimulation will increased cerebral blood flow (CBF)

H0: mean treatment CBF = mean sham CBF

Ha: mean treatment CBF \neq mean sham CBF

Arterial Stiffness

Hypothesis: epidural stimulation will not change arterial stiffness (AS)

H0: mean treatment AS = mean sham AS

Ha: mean treatment AS \neq mean sham AS

Visual Neurocognitive Assessment

Hypothesis: epidural stimulation will improve Stroop score

H0: mean treatment score = mean sham score
Ha: mean treatment score != mean sham score

10.3 ANALYSIS DATASETS

Subjects who complete at least 80% of the protocol will be included in the analysis data set.

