5.4 PARTICIPANT WITHDRAWAL OR TERMINATION

5.4.1 REASONS FOR WITHDRAWAL OR TERMINATION

Participants are free to withdraw from participation in the study at any time upon request. An investigator may terminate participation in the study if:

- Any clinical adverse event (AE), laboratory abnormality, or other medical condition or situation occurs such that continued participation in the study would not be in the best interest of the participant
- The participant meets an exclusion criterion (either newly developed or not previously recognized) that precludes further study participation.

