8.3 TIME PERIOD AND FREQUENCY FOR EVENT ASSESSMENT AND FOLLOW-UP

The occurrence of an AE or SAE may come to the attention of study personnel during study visits and interviews of a study participant presenting for medical care, or upon review by a study monitor. All AEs including local and systemic reactions not meeting the criteria for SAEs will be captured on the appropriate CRF. Information to be collected includes event description, time of onset, clinician's assessment of severity, relationship to study product (assessed only by those with the training and authority to make a diagnosis), and time of resolution/stabilization of the event. All AEs occurring while on study must be documented appropriately regardless of relationship. All AEs will be followed to adequate resolution.

Any medical condition that is present at the time that the participant is screened will be considered as baseline and not reported as an AE. However, if the study participant's condition deteriorates at any time during the study, it will be recorded as an AE. UPs will be recorded in the data collection system throughout the study. Changes in the severity of an AE will be documented to allow an assessment of the duration of the event at each level of severity to be performed. AEs characterized as intermittent require documentation of onset and duration of each episode. The PI will record all reportable events with start dates occurring any time after informed consent is obtained until 7 (for non-serious AEs) or 30 days (for SAEs) after the last day of study participation. At each study visit, the investigator will inquire about the occurrence of AE/SAEs since the last visit. Events will be followed for outcome information until resolution or stabilization.

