The repeated measures ANOVA will be used to compare sham and treatment where alpha is assumed to be 0.025 (two tailed) and power 0.95. The correlation between repeated measures is assumed to be 0.5. The ANOVA residuals will be assessed for normality and the groups will be assessed for homoscedasticity. If there are significant violations of these assumptions then Friedman's test will be used instead. The data will be displayed with means and 95% confidence intervals between treatment and sham for each subject and as a group over time.

Missing data will be analyzed to examine for randomness of omission. If the missing data is determined to be reasonably random, then predictive mean matching will be used for imputation. The distribution of the complete data set will be examined with and without the imputed data.

Data from subjects with incomplete data from dropout will be included in the final analysis unless the subject requested removal of their data. Incomplete data will be pooled per session.

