10.4.4 SAFETY ANALYSES

Safety Endpoints and a summary description are as follows:

- Physical Examination: signs of pressure ulcers, infections, or other relevant emergent findings
- Blood Pressure: change from baseline, before, and after stimulation sessions
- Adverse Event Incidence: as defined by 8.1 Specification of Safety Parameters
- Modified Ashworth Scale Score: changes from baseline, before, and after stimulation settings

Safety endpoints and adverse events will be presented via summary statistics after coding into System Organ Classes (SOCs). As applicable adverse events will only be coded once for each subject. Each adverse event will be described by start date, stop date, severity, relationship, outcome, and duration. AEs will be reported as outlined in 8 ASSESSMENT OF SAFETY.

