10.5 SAMPLE SIZE

Subjects will undergo blinded treatment and sham BMAC testing at each monthly appointment during the course of the trial. Assuming nonattendance to be approximately 25%, we expect subjects to complete at least 9 sessions. With a power of 0.95 and alpha of 0.025 for a two level ANOVA, we assume a correlation among repeat measure of 0.5. By assuming a baseline mean magnitude of 0.3 and a clinically significant change of 0.2 while assuming a within group standard deviation of 0.25 (resulting in an effect size of 0.4), we estimate that we will need at least 56 subjects to demonstrate significance for the primary outcome.

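### The only analysis data set is 80% completers and no safety set is defined, so as written the final safety summaries omit most implanted subjects who stop early for harm

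*Combined protocol and SAP*

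**What the plan says.** Section 10.3 is one sentence: "Subjects who complete at least 80% of the protocol will be included in the analysis data set". It does not say what 80% is a percentage of, and the text provided defines no safety, as-treated or all-implanted set.

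Section 10.4.4 lists four safety endpoints (physical examination, blood pressure, adverse event incidence, Modified Ashworth score). It plans summary statistics by system organ class, with an event coded once per subject where applicable, so incidence is a proportion of subjects. It names no population. Its pointer elsewhere is "AEs will be reported as outlined in 8 ASSESSMENT OF SAFETY", and Section 8 deals with collecting, grading and reporting events.

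For efficacy the plan departs from 10.3. Section 10.4.2 says "Data from subjects with incomplete data from dropout will be included in the final analysis unless the subject requested removal of their data", and 10.4.3 repeats this for the standing and the autonomic endpoints. Section 10.4.4 has no such sentence.

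Section 5.4.1 lets an investigator end participation when staying on no longer serves the subject. The ground reads, in part: "Any clinical adverse event (AE), laboratory abnormality, or other medical condition or situation occurs such that continued participation in the study would not be".

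**The concern.** A safety table for an implanted device should count everyone exposed to the surgery and the device. If entry to the table depends on completing most of the protocol, and an adverse event can stop a subject from completing it, then selection depends on the outcome being measured. A harmed subject who stops early leaves both the numerator and the denominator.

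Section 8.1 calls surgical risk the largest safety concern of the study. Serious surgical and device harms are plausible reasons for stopping early, so a completer rule bears most heavily on them. What is at stake is the final reported incidence, the figure that later investigators and patients would use.

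**Working it through.** **Inputs**
- Number of subjects: at least 56 (10.5).
- Infection incidence with these stimulators: 3% retrospective, 3-4% prospective (2.3.1).
- Monthly visits: first testing visit after surgery at month 3 (7.1.1, device mapping; Table 2), last at month 15 (7.3.5), so 15 - 3 + 1 = 13.
- Unit of the 80% rule: not given. Counting visits is an assumption.

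**1. The plan's 56.** It reproduces from a repeated-measures ANOVA with a two-level between-subject factor, noncentrality N·f²·m / (1 + (m - 1)ρ). With f = 0.1/0.25 = 0.4, m = 9 and ρ = 0.5, this is 56 × 0.16 × 9 / 5 = 16.13. At alpha 0.025 the power is 0.954. Whether that formula suits a within-subject design is a separate matter. Here 56 serves only as the number implanted.

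**2. Who falls below 80%.** 0.80 × 13 = 10.4, so 11 visits are needed. A subject stopping at or before month 12 has at most 10/13 = 77% and is out. One stopping after month 13 has 11/13 = 85% and is in. If 12 visits are counted instead, which fits the 25% and 9 sessions of 10.5 (9/12 = 75%), the threshold is 10 and the cut-off hardly moves.

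**3. Direction.** Let e of N implanted subjects have an event, and let s of those e stop early because of it. With everyone else in the set, the table shows (e - s)/(N - s) instead of e/N. This is lower whenever s > 0 and e < N, because (e - s)N < e(N - s) reduces to e < N. The downward bias applies to the events that lead to stopping. For an unrelated event the smaller denominator raises the rate slightly, for example 2/54 = 3.7% against 2/56 = 3.6%.

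**4. Size, using infection.** Expected cases: 56 × 0.03 = 1.7 to 56 × 0.04 = 2.2, so about 2.

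| Infected subjects stopping before 80% | Completer table | All implanted |
|---|---|---|
| 0 | 2/56 = 3.6% | 2/56 = 3.6% |
| 1 | 1/55 = 1.8% | 2/56 = 3.6% |
| 2 | 0/54 = 0% | 2/56 = 3.6% |

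For a more frequent event (assumed counts), suppose five subjects are affected and three of them stop early. The completer table shows 2/53 = 3.8% against 5/56 = 8.9%.

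**The case against.** The strongest reply is that nothing expressly applies 10.3 to safety. Section 10.1 introduces the statistical plan for the primary, secondary and exploratory outcomes, and 8.1 says that safety is neither a primary nor a secondary endpoint. Section 10.4.4 sends the reader to Section 8, and 8.3 requires that "All AEs occurring while on study must be documented appropriately regardless of relationship". Section 7.3.7 even spares adverse events when it drops unscheduled-visit data from analysis. The application of 10.3 to safety is therefore an inference from its being the only set. But 10.4.4 sits inside Section 10, Section 8 gives no denominator for summaries, and the exception in 7.3.7 concerns visits, not subjects. If 10.3 does not reach safety, the safety summaries have no population at all, and the same sentence is needed.

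Four stronger readings are tempting and are not supported.
- *Harms would be hidden or lost.* They would not. Events are recorded during and shortly after participation (8.3), serious events go to the IRB and FDA within 24 hours (8.4.2), the halting rule has no completion filter (8.5), early terminators are offered a safety visit (7.3.6), and 10.4.4 says each event will be described.
- *The FDA checkpoint is affected.* Section 5.3 covers the 10 recruited subjects after month 6. By then a subject has at most 4 of 13 visits, so a visit-based 80% rule could not be met and cannot be intended there.
- *Nobody who stops early can reach 80%.* Step 2 shows that a late stopper can.
- *Two thirds of subjects vanish from the safety tables.* Section 10.5 says "Assuming nonattendance to be approximately 25%, we expect subjects to complete at least 9 sessions". With independent misses over 13 visits, P(at least 11 attended) is 0.333, about 19 of 56. That concerns missed visits. Absence unrelated to harm removes cases and non-cases alike, so it costs precision but does not produce the downward bias.

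It is also fair to say that no section makes infection end participation, and 5.4.2 says that withdrawal does not mean automatic device removal. The last row of the table is a worst case.

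**Conclusion.** The concern holds as a defect in how the final safety summaries are defined. The plan's only stated population is completers, safety has no exception, and applying the text literally makes inclusion depend on not having been stopped early by harm. The bias is downward for the events that cause stopping. For infection it runs from none (3.6% shown as 3.6%) through half (1.8%) to complete (0%), according to how many of about 2 affected subjects stop early.

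These figures assume 56 implanted subjects, the protocol's 3-4% infection rate, 80% counted in visits, and all other subjects meeting the threshold. The direction of the bias needs only that some affected subjects fall below the threshold. The conclusion is confined to the final summaries and their denominators.

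**What to change.** Add to 10.3 and 10.4.4 text to this effect:

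> The safety analysis set is every subject in whom implantation was started, regardless of completion or compliance. Adverse events, blood pressure, Modified Ashworth score and physical examination findings are all summarised in this set. The 80% rule does not apply to safety.

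In the same edit, reconcile 10.3 with the dropout sentences in 10.4.2 and 10.4.3, which keep subjects that 10.3 would remove. If the 80% rule survives for any efficacy analysis, state its unit and which analysis it governs.

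The cost is a few sentences. No new data are needed, because events are already recorded for all subjects on study and non-compliant subjects stay in follow-up (8.3, 10.4.5). The sample size does not change. The downside for the sponsor is that reported adverse event rates may be less favourable.

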10.4 DESCRIPTION OF STATISTICAL METHODS

10.4.1 GENERAL APPROACH

This study represents a single-arm quasi-experimental, multiple, sham-controlled crossover study. This design is possible because of the rapid onset and offset of the effect of epidural stimulation as previously reported. This protocol provides the opportunity to test outcome measures intensely in each individual subject over different stimulation settings with sham control longitudinally. The intention of the longitudinal assessments is to search for improvements over time with increased understanding of the stimulation parameter space. As such most outcomes utilize the repeated measures ANOVA.

Baseline data relevant to spinal cord injury movement and its adverse effects will be measured in the hopes of providing guidance for future generalizability. Descriptive statistics will be reported as means with standard deviations. Tests will be considered statistically significant when alpha is less than 0.05 for two-tailed tests. All assumptions for statistical tests will be evaluated before use of the test and corrected if necessary and possible.

10.4.2 ANALYSIS OF THE PRIMARY EFFICACY ENDPOINT(S)

The primary outcome is volitional movement as measured by the brain motor control assessment (BMCA). The BMCA uses surface electromyography (sEMG) to track changes in muscle amplitudes relative to a population control in a normalized fashion. In this protocol, the lower extremity BMCA is used to track progress during the trial and is reported as a vector, which consists of the magnitude of the response vector (RV) and the similarity index (SI). The response vector is composed of the magnitudes of the sEMG where each dimension is an included muscle. The similarity index is the inner product of the normalized response vector in controls for a single maneuver with the normalized RV from the subject for that maneuver. The RV is reported in microvolts while the SI is reported as a value between 0 and 1, both continuous variables. As a pair, these are referred to as the voluntary response index (VRI).

The VRI for each maneuver will be averaged over all of the muscle groups at each appointment, resulting in a single sham vector and a single stimulation vector for each regularly scheduled appointment. By design, subjects undergoing the protocol should have response magnitudes and SI of 0 as baseline readings. By normalizing the VRI to (200, 1), it is possible to report a clinically significant change. For example, computing the normalized magnitude for a response magnitude of 50 uV and a SI of 0.2 would result in $\sqrt{(50/200)^2 + (0.2/1)^2} = 0.32$. Based on the limited data using this particular outcome, we feel a clinically significant change would be a distance of 0.2. This allows muscles groups to coordinate or improve in magnitude.

The primary outcome is whether subjects regain volitional movement during epidural stimulation. The hypothesis is then that the VRI should be higher during blinded treatment when compared to sham stimulation. While the time-course of change and measurements of plasticity are also interesting, the very small amount of pre-existing preliminary data available encourages efforts to focus on major changes in the primary outcome. For each subject,

we assume subjects will be able to attend at least 10 appointments, and, therefore, undergo 10 BMAC tests, resulting in 10 VRIs during treatment and sham.

The repeated measures ANOVA will be used to compare sham and treatment where alpha is assumed to be 0.025 (two tailed) and power 0.95. The correlation between repeated measures is assumed to be 0.5. The ANOVA residuals will be assessed for normality and the groups will be assessed for homoscedasticity. If there are significant violations of these assumptions then Friedman's test will be used instead. The data will be displayed with means and 95% confidence intervals between treatment and sham for each subject and as a group over time.

Missing data will be analyzed to examine for randomness of omission. If the missing data is determined to be reasonably random, then predictive mean matching will be used for imputation. The distribution of the complete data set will be examined with and without the imputed data.

Data from subjects with incomplete data from dropout will be included in the final analysis unless the subject requested removal of their data. Incomplete data will be pooled per session.

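### Unequal variance sends the paired primary comparison to Friedman's test: the check is not needed, and with two conditions the fallback is a sign test that can lose power when sham spread is the smaller or when a minority gain well over 0.2

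*Combined protocol and SAP*

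**What the plan says.** Section 10.2 states the primary hypothesis on means: "H0: mean treatment VRI magnitude = mean sham VRI magnitude". Section 10.4.1 calls the design a "single-arm quasi-experimental, multiple, sham-controlled crossover study". Section 10.4.2 reduces each visit to two conditions, "resulting in a single sham vector and a single stimulation vector for each regularly scheduled appointment".

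The test follows in the same section: "The repeated measures ANOVA will be used to compare sham and treatment where alpha is assumed to be 0.025 (two tailed) and power 0.95". Two checks come next: "The ANOVA residuals will be assessed for normality and the groups will be assessed for homoscedasticity". The consequence is "If there are significant violations of these assumptions then Friedman's test will be used instead".

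No variance test, threshold or blocking unit is named. Section 10.4.1 promises in general that failed assumptions will be corrected where that can be done, but names no correction. Section 10.4.3 repeats the checks and the switch for Standing Training and for Autonomic Function.

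**The concern.** Sham and stimulation come from the same subject at the same visit. The two-level contrast is therefore a test on within-subject differences, and nothing in it needs the two sets of values to have equal variance. With two levels, sphericity is automatic. The variance check can thus discard a valid test.

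What replaces it is weaker and answers a different question. With two conditions, Friedman's test ranks each pair 1 and 2 and so keeps only the sign of the difference. Section 10.4.2 defines clinical relevance as a size (a distance of 0.2) and section 10.2 sets the hypothesis on means. The fallback tests neither.

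There is reason to expect unequal spread. Section 10.4.2 says "By design, subjects undergoing the protocol should have response magnitudes and SI of 0 as baseline readings". If sham readings stay near that floor while stimulation readings vary between subjects, the two variances differ. At stake is a real benefit, perhaps concentrated in some subjects, being missed because of a check that the design does not need.

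**Working it through.** **Inputs from the documents.** n = 56, alpha 0.025 two-tailed, power 0.95, SD 0.25, correlation 0.5, gain 0.2, 9 sessions (10.4.2 and 10.5).

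**Assumptions, not in the documents.** The share of subjects who respond, the size of their gain, any sham SD other than 0.25, and the check itself (median-centred Levene at 5%).

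**1. The plan's own figure.** f = (0.2/2)/0.25 = 0.4. In the between-group form of repeated measures ANOVA, lambda = f²·N·m/(1 + (m − 1)·rho) = 0.16 × 56 × 9/(1 + 8 × 0.5) = 80.64/5 = 16.1 on 1 and 54 df. Power is 0.954, so N = 56 reproduces. The within-subject form with two measurements gives 27. The sample size therefore treats sham and stimulation as independent groups, where equal variance would matter. The trial described in 10.4.1 and 10.4.2 is paired.

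**2. Is the check needed?** Under the null, with stimulation SD 1, 2 and 3 times sham SD, the paired t test rejects at 0.024, 0.025 and 0.027 (nominal 0.025). At sham/stimulation SDs of 0.15/0.25 with no effect, its level is 0.022, yet Levene trips in 95% of trials.

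**3. What Friedman becomes.** With two conditions, Q = (n₊ − n₋)²/n on 1 df. At n = 56 it needs at least 37 positive differences: (37 − 19)²/56 = 5.79 (exact level 0.022).

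**4. Uniform gain.** The SD of the difference is 0.25 × √(2 × (1 − 0.5)) = 0.25, so the standardised gain is 0.2/0.25 = 0.8. P(positive) = Φ(0.8) = 0.788, and P(at least 37 of 56) is about 0.99.

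**5. The whole gated procedure.** Simulation with one value per subject and condition and n = 56. Gated means paired t unless Levene trips, then Friedman.

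| Scenario | Check trips | Gated power | Paired t always |
|---|---|---|---|
| 50% gain 0.2, equal SDs | 4–5% | 0.67 | 0.68 |
| 50% gain 0.4, equal SDs | 45% | 0.94 | 0.99 |
| 30% gain 0.4, equal SDs | 31% | 0.60 | 0.72 |
| 30% gain 0.67, equal SDs | 89% | 0.56 | 0.95 |
| 50% gain 0.2, SDs 0.15/0.25 | 95% even with no effect | 0.55 | 0.78 |

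**6. Dependence on how the check is run.** With nine visits and responders gaining 0.2, a variance check on subject means trips in 5% of trials or fewer. On visit-level values it trips in 20% to 38% when 20% to 75% of subjects respond.

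**7. The normality route.** In the nine-visit simulation, a normality check on subject-level differences trips in 16% to 34% of trials at a responder gain of 0.2 (20% to 75% responders), and almost always at a gain of 0.4 in 20% to 50% of subjects. With one value per subject and a gain of 0.4 in 30% or 50%, it trips at about its nominal rate (7% and 5%). Removing only the variance trigger would leave this path to Friedman open.

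**The case against.** The strongest reply is that at the plan's own effect size the rule does little harm. With equal SDs of 0.25 and one value per subject and condition, responders who gain 0.2 do not trip the check above its nominal rate, and power is almost unchanged. Under a uniform gain of 0.2, even SDs of 0.15/0.25, which cause a switch in 95% of trials, leave Friedman at 0.998 against 1.000. This stands, and it limits the point.

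A reader might infer more than the documents support, in three ways.

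- *Any partial response trips the check.* It does not. It takes gains well above 0.2, a sham spread below the stimulation spread, or a check run on visit-level values.
- *The stated 0.95 power fails once Friedman is used.* Under a uniform gain of 0.2 the fallback has about 0.99.
- *Power falls to about a third.* Friedman alone does reach about 0.33 when 25% of subjects respond and the average gain is held at 0.2. Each responder must then gain 0.2/0.25 = 0.8, four times the clinically significant change, and nobody else gains anything. No responder share is documented.

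Other parts of the reply also stand. Section 10.5 assumes a baseline mean of 0.3 with SD 0.25, which does not fit readings of 0, so a smaller sham spread is plausible but not established. If non-responders tied exactly at zero, the loss would shrink. With heavy-tailed differences a sign test can beat the t test. The secondary endpoints share the wording, but no responder or variance figures support a power claim there, and 10.4.9 treats them as preliminary.

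The blocking unit is also open. With subject-visits as blocks (56 × 9 = 504), Friedman's power is close to that of the t test. Its type I error, however, rises to 0.08 or 0.20 if subject-level differences vary around zero with an assumed SD of 0.1 or 0.2. That is no rescue.

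**Conclusion.** The point holds in a limited form. Equal variance between sham and stimulation is not an assumption of this comparison and should not decide the primary test. The test it leads to discards the size of the gain and does not address the stated hypothesis on means. Both statements follow from the design and need no simulation.

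The size is conditional. With subjects as blocks and Levene at 5%, the loss runs from negligible (0.67 against 0.68) to serious (0.56 against 0.95, or 0.55 against 0.78). The serious cases need either a minority with gains well above 0.2 or a sham SD below the stimulation SD. Neither is documented and neither is ruled out. This is worth correcting before unblinding; it does not show that 56 subjects are too few.

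**What to change.** In 10.4.2:

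- Delete equal variance between sham and stimulation as a trigger.
- Define the primary quantity as each subject's stimulation-minus-sham difference in normalised VRI magnitude, averaged over attended visits.
- Test its mean with a paired (one-sample) t test, supported by a sign-flip permutation p-value. State that the paired mean test decides.
- As the fallback for non-normality, replace Friedman's test with the Wilcoxon signed-rank test on the same differences, and state how non-normality will be judged. This closes the second route to Friedman. In the scenario with 30% gaining 0.67, signed-rank power is 0.86 against 0.47 for Friedman.

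Apply the same wording to the two-condition comparisons under Standing Training and Autonomic Function in 10.4.3.

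The cost is SAP wording only, with no added subjects, visits or data. The downside is that signed-rank assumes roughly symmetric differences, and it is still less powerful than the paired t test when a few subjects gain a great deal. It should remain a fallback.
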